### Secondary endpoints

#### a. Efficacy:

- Survival rate (SR) at 6 months, 9 months, and 12 months
- Time to progression (TTP): Duration from start of study treatment to time of disease progression
- Progression-free survival (PFS): Duration from start of study treatment to PD or death (regardless of cause), whichever comes first
- Duration of response (DOR): Duration from the first observation of at least PR to time of disease progression, or deaths due to disease progression, whichever occurs first
- CBR: Proportion of patients who achieve sCR, CR, VGPR, PR, or minimal response (MR)
- DCR: Proportion of patients who achieve sCR, CR, VGPR, PR, MR, or stable disease (SD; for a minimum of 12 weeks)
- OS (Kaplan-Meier estimates)
- MRD in patients who achieve CR and sCR
- The effect of risk factors stratification based on fluorescence in situ hybridization (FISH) on clinical efficacy, including del 13, del 17p13, t(4;14), t(14;16), 1q21 amplification

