#### 6.2.2. Secondary Endpoints

a. Efficacy:

- SR at 6 months, 9 months, and 12 months
- TTP: Duration from start of study treatment to time of disease progression
- PFS: Duration from start of study treatment to PD or death (regardless of cause), whichever comes first
- DOR: Duration from the first observation of at least PR to time of disease progression, or deaths due to disease progression, whichever occurs first.
- CBR: Proportion of patients who achieve sCR, CR, VGPR, PR, or minimal response (MR)
- DCR: Proportion of patients who achieve sCR, CR, VGPR, PR, MR, or stable disease (SD; for a minimum of 12 weeks)
- OS (Kaplan-Meier estimates)
- MRD in patients who achieve CR and sCR
- The effect of risk factor stratification based on fluorescence in situ hybridization (FISH) on clinical efficacy, including del 13, del 17p13, t (4;14), t (14;16), 1q21 amplification

b. Safety and tolerability

c. PK: including but not limited to ATG-010 Cmax and tmax

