### **13.3.4. Secondary Endpoints**

The following secondary efficacy endpoints for the mITT and PP populations will be analyzed separately.

- Survival rate (SR) at 6, 9, and 12 months
- Duration of response (DOR) = Duration from the first observation of at least partial response (PR) to time of disease progression (PD) or death due to PD, whichever comes first. DOR for death due to any reasons other than PD will be censored.
- Clinical benefit rate (CBR) = CBR+minimal response [MR], and duration of clinical benefit (duration from the first observation of at least MR to PD or death due to PD, whichever comes first). Duration of clinical benefit for death due to any reasons other than PD will be censored.
- Disease control rate (DCR) = CBR+stable disease [SD; for at least 12 weeks])
- Progression-free survival (PFS) = Duration from start of study treatment to PD or death [irrespective of cause of death], whichever comes first)
- Time to progression (TTP) = Duration from start of study treatment to time of PD
- Overall survival (OS) = Duration from start of study treatment to death

The Kaplan-Meier (KM) method will be used to analyze the time to event endpoints (including duration of response, PFS, TTP, and OS), including the median estimate, 25th and 75th percentiles, and two-sided 95% CIs. The CBR and DCR will be summarized using two-sided 95% confidence intervals.

In addition, the following secondary endpoints of safety and tolerability will be analyzed using the Safety Analysis Set.

- Safety and tolerability will be analyzed per National Cancer Institute (NCI)-Common Terminology Criteria for Adverse Events (CTCAE) v 4.03.
- The ATG-010 PK profile of this patient population will be described.
- Cytogenetic and fluorescence in situ hybridization (FISH) prognostic markers, including chromosomal aberrations [e.g., del17p, t(4;14), t(14;16), del13] and other cytogenetic categories of MM.

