### Appendix 3. International Myeloma Working Group Response Criteria, Myeloma

**Table 10: International Myeloma Working Group Response Criteria (Kumar 2016)**

Standard IMWG Response Criteria 	
Response subcategory	Response criteria
Complete Response (CR)	Negative IFE of serum and urine, disappearance of any soft tissue plasmacytomas (SPD), and <5% plasma cells in bone marrow aspirates
Stringent Complete Response (sCR)	CR as defined above plus normal FLC ratio  and absence of clonal cells in bone marrow biopsy by immunohistochemistry ( $\kappa/\lambda$ ratio $\leq 4:1$ or $\geq 1:2$ for $\kappa$ and $\lambda$ patients, respectively, after counting $\geq 100$ plasma cells  )
Very Good Partial Response (VGPR)	Serum and urine M-protein detectable by IFE but not on electrophoresis, or $\geq 90\%$ reduction in serum M-protein plus urine M-protein level $<100$ mg per 24 hours
Partial Response (PR)	$\geq 50\%$ reduction of serum M-protein plus reduction in 24-hour urine M-protein by $\geq 90\%$ or to $<200$ mg per 24 hours. If the serum and urine M-protein are unmeasurable, a $\geq 50\%$ decrease in the difference between involved and uninvolved FLC levels is required in place of the M-protein criteria. If serum and urine M-protein are unmeasurable, and serum FLCs are also unmeasurable, $\geq 50\%$ reduction in plasma cells is required in place of M-protein, provided baseline bone marrow plasma cell percentage was $\geq 30\%$ . In addition to the above criteria, if present at baseline, a $\geq 50\%$ reduction in the size (SPD) of soft tissue plasmacytomas is also required 
Minimal Response (MR)	$\geq 25\%$ but $<49\%$ reduction of serum M-protein, and reduction in 24-h urine M-protein by 50-89%. In addition to the above criteria, if present at baseline, a $\geq 50\%$ reduction in the size (SPD) of soft tissue plasmacytomas is also required 
Stable Disease (SD)	Not recommended for use as an indicator of response; stability of disease is best described by providing the TTP estimates. Not meeting criteria for CR, VGPR, PR or progressive disease

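### Table 10 leaves falls just short of PR in neither MR nor PR, and Section 13.3.4 does not say how TTP treats deaths; both are minor and ORR is unaffected

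*Combined protocol and SAP*

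**What the plan says.** **Response bands (Appendix 3, Table 10).** PR needs a serum fall of at least 50%, plus a urine fall of at least 90% or to below 200 mg/24 h. MR needs a fall of at least 25% but under 49%, continuing "reduction of serum M-protein, and reduction in 24-h urine M-protein by 50-89" per cent. SD is residual: it takes whatever does not meet CR, VGPR, PR or PD. MR counts towards CBR (Section 6.2.2: "CBR: Proportion of patients who achieve sCR, CR, VGPR, PR, or minimal response (MR"; the synopsis agrees) and starts the duration of clinical benefit in Section 13.3.4.

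**TTP.** The synopsis ("Time to progression (TTP): Duration from start of study treatment to time of disease progression"), Section 6.2.2 ("TTP: Duration from start of study treatment to time of disease progression") and Section 13.3.4 ("Time to progression (TTP) = Duration from start of study treatment to time of PD") agree with one another: the only event is PD. None of them mentions deaths. In the Section 13.3.4 list, DOR runs "to time of disease progression (PD) or death due to PD, whichever comes first" and duration of clinical benefit is the "duration from the first observation of at least MR to PD or death due to PD, whichever comes first". Both expressly censor other deaths. PFS counts every death. Kaplan-Meier is prescribed for the time-to-event endpoints.

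**Clerical.** Section 13.3.4 gives "Clinical benefit rate (CBR) = CBR+minimal response [MR", which is circular.

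**The concern.** The bands of an ordered response scale should meet. If MR stops at 49% and PR starts at 50%, a patient one step from PR is graded SD, below a patient with a 30% fall. That patient can drop out of CBR and out of duration of clinical benefit. DCR changes only if the resulting SD lasts under 12 weeks.

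For TTP, a myeloma death without documented PD ends DOR as an event but is not an event for TTP. Under Kaplan-Meier it would be censored. That censoring is informative, because the patient has in effect progressed, and it can only raise the TTP curve. No reason is given for treating the same death differently within one list. Only descriptive secondary endpoints are at stake.

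**Working it through.** **1. Primary design.** Inputs (Sections 13.1.2 and 13.3.3): N=82, ORR 28% against 15%, one-sided alpha 0.025, success if the lower 95% limit exceeds 15%. By the exact binomial, the smallest r with P(X ≥ r | 0.15) ≤ 0.025 is 20. This gives alpha 0.0172 and power 0.8012, so N=82 reproduces. The Clopper-Pearson lower limit is 15.58% at 20/82 and 14.56% at 19/82. ORR uses sCR, CR, VGPR and PR only, so neither MR nor TTP enters it and these figures stay as they are.

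**2. The bands side by side.**

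| Component | MR | PR | Unassigned |
|---|---|---|---|
| Serum fall | ≥25% to <49% | ≥50% | 49% to <50%, including exactly 49% |
| Urine fall | 50-89% | ≥90%, or to <200 mg/24 h | above 89% to <90%, unless under 200 mg/24 h remains |

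A urine fall above 89% leaves less than 11% of baseline. The 200 mg route to PR's urine condition is therefore always met when baseline is below 200/0.11 = 1,818 mg/24 h.

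**3. Size of the serum gap.** One patient is 1/82 = 1.2 points of CBR. For example, 32/82 = 39.0% against 33/82 = 40.2%, while the 95% CI for 32/82 is 28.4% to 50.4%.

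For an expected count I take the MR share from STORM (Section 4.2.2, Table 3). CBR is 19 + 29 = 48 and ORR is 15 + 17 = 32, so there are 16 MRs among 122 patients, of which 29 − 17 = 12 are outside the FLC group. Assumption: MRs are spread evenly over the 24 points from 25% to 49%, with the same density in the one-point gap.

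- All MRs: 82 × 16/122 = 10.75; 10.75/24 = 0.45 patients (0.55 points of CBR); chance of at least one 1 − exp(−0.448) = 36%.
- Non-FLC MRs: 82 × 12/122 = 8.07; 8.07/24 = 0.34 patients (0.41 points); 1 − exp(−0.336) = 29%.

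**4. Values in the gap are not patients lost.** CBR counts patients who achieve MR or better at any time. Assessments repeat each cycle, and a category needs two consecutive assessments (Table 10, footnote 1). Serum falls of 30%, 40% and then 49.5%, with the urine condition met, still give a confirmed MR from the first two. Under the assumption in step 3, the counts there are therefore upper limits on patients lost through the serum gap.

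**5. TTP.** The documents do not give the number of PD deaths without documented PD. Illustration only, assuming a 4.7-month median to first event (a PFS figure quoted for STORM in Section 4.2.2, population unclear), constant hazard, and 82 patients followed for 12 months:

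- First events: 82 × (1 − 2^(−12/4.7)) = 68.0.
- If k of these are PD deaths without documented PD, the PD-only median is 4.7/(1 − k/68.0).

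| k | PD-only median (months) | Mean simulated shift (months) |
|---|---|---|
| 0 | 4.70 | – |
| 1 | 4.77 | +0.10 |
| 2 | 4.84 | +0.21 |
| 4 | 4.99 | +0.38 |
| 8 | 5.33 | +0.71 |

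The simulated shifts come from 4,000 trials. They are slightly larger than the formula gives, and no trial gave a shorter median. For scale, the 95% sampling range of the median itself was 3.3 to 6.2 months. With the same censoring dates, a TTP that counts PD deaths lies between PFS and TTP as written, so the effect cannot exceed the reported gap between those two.

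**The case against.** **On the bands.** The printed limits may be whole-percent bands. Under that reading the urine gap closes, but a serum fall of exactly 49% is still unassigned. If a sign was lost in the PDF text and MR should read up to and including 49%, values between 49% and 50% are still uncovered. Response is assessed by the IRC under IMWG criteria, and Table 10 refers questions of interpretation to the guideline, so the IRC may grade such a patient sensibly anyway. That limits the harm, but it does not make the printed table right. A reader might infer that every patient with a value in the gap is lost from CBR. The two-assessment rule does not support that (step 4).

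**On TTP.** A reader might infer that the TTP definition is simply wrong. The documents do not support this. TTP is defined the same way three times, it is a different endpoint from DOR, and nothing requires the two to share an event set. PFS and OS already count every death. Section 13.1.1 also defers analysis details to a SAP whose rules are not in the text available here.

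Several provisions keep undocumented PD rare: myeloma tests at end of treatment and at progression, disease status collected every 3 months, and exclusion of patients with life expectancy under 4 months. One route stays open. Every category except SD is unconfirmed until a second test (Table 10, footnote 3), so a patient may die in between. Section 9.3 allows both samples on one day, which can close even that window.

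Counting PD deaths has a cost too. Cause of death matters today only for patients with MR or better, and it would then matter for all 82. Section 12.1 keeps fatal progression out of SAE reporting, and the follow-up items in Table 1, footnote 13, do not list cause of death. What remains is that the difference is unexplained and the TTP rule for deaths is unstated.

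**Conclusion.** Low severity throughout.

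1. The MR bands are wrong as written. The serum gap is one percentage point wide. Its expected occupancy is 0.45 patients (0.34 outside the FLC group), an upper limit on the expected number lost from CBR. This rests on the STORM MR share and an even spread across the band. The urine gap is of the same kind and was not sized.
2. TTP is inconsistent with DOR and duration of clinical benefit on deaths due to PD, and no rule for deaths is stated. The direction of any effect is certain (TTP no shorter), its size is unknown, and it may be near zero. This is a gap in specification, not a demonstrated error.
3. The CBR formula in Section 13.3.4 is a slip. The synopsis and Section 6.2.2 show that ORR + MR is meant.

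Nothing here bears on the primary analysis or the sample size.

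**What to change.** - **Table 10.** Run the MR bands up to the PR floors: serum ≥25% to <50%, urine 50% to <90%, after checking the cited IMWG guideline. Leave the rest of the row alone. Discordant serum and urine falls, unmeasurable urine protein and FLC-only disease should follow the guideline, through the IRC Charter or the SAP, before database lock. MR is also used in inclusion criterion 3, so confirm that the reading of prior responses is unaffected. The 25% lower bound does not move; only a prior best fall inside a gap would be read differently.
- **Section 13.3.4, TTP.** State how deaths are handled. Either match DOR (PD or death due to PD, other deaths censored) and align the synopsis and Section 6.2.2, or keep PD only and give the DOR-style version as a sensitivity analysis. If the SAP already settles this, align the protocol text with it.
- **Section 13.3.4, CBR.** Correct the formula to ORR + MR.

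The cost is a few words in one table row and in the endpoint definitions. The one real burden is cause-of-death attribution for all patients if PD deaths enter TTP, in the main or the sensitivity analysis. The source and the assessor for that attribution should then be named.

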### 13.3.5. Pharmacokinetic

Plasma analysis will be performed using validated High-Performance Liquid Chromatography-Tandem Mass Spectrometry (HPLC/MS-MS) to determine the blood concentration of ATG-010. The drug concentrations will be used to plot tables and graphs for each subject's drug concentration-time data and average drug concentration-time data. The following PK parameters of ATG-010 will be obtained by analyzing effective blood drug concentration data:

- Maximum drug concentration ( $C_{max}$ , observed value)
- Time to maximum drug concentration ( $T_{max}$ , observed value)
- Areas under the drug concentration-time curve from time 0 to the last measurable concentration and to infinity ( $AUC_{0-last}$  and  $AUC_{0-\infty}$ , respectively)
- Terminal elimination half-life ( $T^{1/2}$ )
- Plasma clearance (CL)
- Volume of distribution (Varea)

### 13.3.6. Safety Data

Safety analysis will be performed on the total patient population receiving any dose of study treatment, and the results will be listed. Each patient's original dose level will be used for safety analysis; in the primary safety analysis, dose escalation or reduction will not be independently classified. An additional exploratory assessment of the effects of dose modification on safety may be performed.

#### 13.3.6.1. Adverse Event

AEs will be coded per Medical Dictionary for Regulatory Activities (MedDRA) and presented in tables and listings per MedDRA System Organ Class (SOC) and Preferred Term (PT).

Events deemed to be treatment-emergent will be included in AE analysis, where "treatment-emergent" refers to any AE or exacerbation of a pre-existing disease that emerges or after the first dose of study treatment or within 30 days after last dose of study treatment, or any event that emerges prior to the end of study and is considered drug-related by the Investigator. AEs with partial dates available will be assessed using the existing date information to determine if they are treatment-emergent; AEs with dates completely missing will be assumed as treatment-emergent. No formal hypothesis testing will be performed on the incidence rates of AEs.

AEs will be summarized per patients' incidence rates; therefore, each patient will be counted only once for a given AE (Preferred Term) in any listing. The number and percentage of patients with any treatment-emergent adverse event (TEAE) will be summarized per treatment group, and stratified per SOC and Preferred Term. The number and percentage of patients with TEAE that is assessed as at least possibly related to treatment by the Investigator will also be listed. The number and percentage

of patients with any Grade  $\geq 3$  TEAE will be listed in the same way.

The Investigator will assess the causal relationship between an AE and the study drug as not related or related. If a patient experiences the same AE repeatedly, events with the highest severity and/or with a strong causal relationship with treatment will be used for the purpose of tabulations.

All SAEs reported will be listed.

All AEs (emerging during and after treatment) will be presented in the individual patient data listings and will be classified per treatment, patient, and study day. In addition, individual patient listings will be provided for the following events: deaths, SAEs, and AEs leading to withdrawal.

#### **13.3.6.2. Laboratory Data**

Clinical laboratory test values will be presented using traditional units of International System of Units (SI). For various clinical laboratory parameters (including hematology, clinical chemistry, coagulation, and urinalysis), the actual value and change from baseline (Day 1, prior to first dose of study drug) to each on-study assessment will be summarized. In the presence of duplicate values, the last non-missing value of each study date/time will be used. If Day 1 data of a pre-defined patient/parameter are not available, the baseline values will be replaced with the screening values.

Severity of selected clinical laboratory measures (e.g., measures with corresponding CTCAE grading) will be determined per CTCAE v4.03 criteria. Laboratory values at CTCAE Grade  $\geq 3$  will be presented in data listings. Shift tables will be generated to list the changes from baseline to worst on-study value and from baseline to last on-study value relative to CTCAE classification.

#### **13.3.6.3. Vital Signs, Physical Examination and ECOG Performance Status**

For vital signs, the actual value and change from baseline (Day 1) to each study assessment will be summarized. Shift tables will be generated to list the changes from baseline to worst on-study value and to last on-study ECG performance status. The individual patient listing of all vital sign measurements and ECOG performance status scores will be presented in data listings.

The physical examination results at Screening and changes in the physical examination results during the study will be summarized. All physical examination results will be presented in the individual patient data listings.

#### **13.3.6.4. ECG Results**

ECG results, including heart rate and PR, QRS, QT, and QTc (calculated by Fridericia's correction formula) intervals, will be summarized in a descriptive manner. If Bazett's correction formula is already entered by the study site, Fridericia-corrected QTc interval (QTcF) will be deduced using the following formula:  $QT/(RR^{1/3})$ , where, RR=60/heart rate. Actual values and changes from baseline will be reported at each study visit.

Each patient's ECG data will be provided in a data listing.

#### **13.3.6.5. Concomitant meds**

Concomitant medications used will be included in the individual patient data listings.

### **13.3.7. Missing Data Handling Procedures**

The missing data handling procedures will be performed following the SAP.

### **13.4. Changes in Study Conduct or Planned Analyses**

All deviations from the original statistical analysis plan will be recorded and presented in the final clinical study report.

## 14. Regulatory Considerations

### 14.1. International Conference on Harmonization – Good Clinical Practices

The study conduct, assessment and recording procedures defined in this study protocol are designed to ensure the study is conducted by Antengene, authorized representatives, and Investigators in compliance with the Good Clinical Practice (GCP) in the International Council for Harmonisation of Technical Requirements for Pharmaceuticals for Human Use (ICH) Guidelines E6 and the general ethical principles in the Declaration of Helsinki. The study will be implemented after approval by IRB/EC. Investigator will implement all aspects of this study in accordance with the applicable laws of the country or region in which related regulatory authorities are located.

### 14.2. Investigator's Responsibilities

Investigator's responsibilities are stipulated in ICH GCP guidelines and local laws and regulations. Antengene staff or authorized representatives will assess and approve Investigators, while investigators will be responsible for choosing the study personnel.

Investigators should ensure that all personnel assisting in the study work have a full understanding of the study protocol, amendments, study treatment, and study-related responsibilities and functions. Investigators should be responsible for keeping the list of other qualified personnel assisting Investigators and delegated with important study-related responsibilities.

Investigators are responsible for keeping the records of all subjects who have signed informed consent forms (ICF) and accepted for study screening. For screen-failure subjects, the reason must be recorded in their source documents.

Investigators or designated personnel must be present during the monitoring period to check data, solve queries, and facilitate direct access to view subjects' records (e.g., medical records, outpatient medical records, inpatient medical records, and study-related medical records) as to complete the source data verification. Investigators must ensure CRFs are filled and the queries are resolved in a timely and accurate CRF manner.

### 14.3. Subject Information and Informed Consent

Investigator must obtain the informed consent of legal representative before performing any study-related procedures.

The record of informed consent performed before the study subject enters the study and the process of obtaining informed consent should be kept in the subject's source documents, including relevant dates. The original copy of ICF signed and dated by the study subject and the personnel explaining the ICF before the subject enters the study must be kept in the Investigator's study file, with a copy provided to the subject. In addition, if the study protocol is amended and the amendment has an impact on the content of informed consent, the ICF must be modified accordingly. After the study protocol is amended, subjects participating in the study must agree to sign the modified ICF. The original copy of modified ICF signed and dated by the study subject and the personnel explaining the ICF must be kept in the Investigator's study file, with a copy provided to the subject.

